6.2.2. Primary Safety Endpoint and Safety Considerations

Primary safety endpoint: The overall incidence and severity of all adverse events including clinically significant thrombocytopenic events using Common Toxicity Criteria v 4.0.

An adverse event is any untoward medical occurrence that may present during treatment with a pharmaceutical product but which does not necessarily have a causal

relationship with this treatment. Adverse drug reaction is a response to a drug which is noxious and unintended and which occurs at doses normally used in man for prophylaxis, diagnosis, or therapy of disease or for the modification of physiologic function.

All “suspected adverse reactions” (as defined in 21 CFR 312.32(a)) will be captured in the case report forms. For abnormal chemical values grade 3 or 4, the apogee will be reported per course in the CRF.

Assessing causal connections between agents and disease is fundamental to the understanding of adverse drug reactions. In general, a drug may be considered a contributory cause of an adverse event if, had the drug not been administered, 1) the event would not have happened at all, 2) the event would have occurred later than it actually did, or 3) the event would have been less severe.

The Investigator or physician designee is responsible for verifying and providing source documentation for all adverse events and assigning the attribution for each event for all subjects enrolled on the trial. Protocol specific data and adverse events will be entered into PDMS/CORe, the electronic case report form for this protocol.

6.2.2.1. Serious Adverse Event Reporting (SAE)

An adverse event or suspected adverse reaction is considered “serious” if, in the view of either the investigator or the sponsor, it results in any of the following outcomes:

- Death
- A life-threatening adverse drug experience – any adverse experience that places the patient, in the view of the initial reporter, at immediate risk of death from the adverse experience as it occurred. It does not include an adverse experience that, had it occurred in a more severe form, might have caused death.
- Inpatient hospitalization or prolongation of existing hospitalization
- A persistent or significant incapacity or substantial disruption of the ability to conduct normal life functions.
- A congenital anomaly/birth defect

Important medical events that may not result in death, be life-threatening, or require hospitalization may be considered a serious adverse drug experience when, based upon appropriate medical judgment, they may jeopardize the patient or subject and may require medical or surgical intervention to prevent one of the outcomes listed in this definition. Examples of such medical events include allergic bronchospasm requiring intensive treatment in an emergency room or at home, blood dyscrasias or convulsions that do not result in inpatient hospitalization, or the development of drug dependency or drug abuse (21 CFR 312.32).

- Important medical events as defined above may also be considered serious adverse events. Any important medical event can and should be reported as an

SAE if deemed appropriate by the Principal Investigator or the IND Sponsor, IND office.

All events occurring during the conduct of a protocol and meeting the definition of a SAE must be reported to the IRB in accordance with the timeframes and procedures outlined in "The University of Texas M. D. Anderson Cancer Center Institutional Review Board Policy for Investigators on Reporting Unanticipated Adverse Events for Drugs and Device. Unless stated otherwise in the protocol, all SAEs, expected or unexpected, must be reported to the IND Office, regardless of attribution (within 5 working days of knowledge of the event).

All life-threatening or fatal events, that are unexpected, and related to the study drug, must have a written report submitted within **24 hours** (next working day) of knowledge of the event to the Safety Project Manager in the IND Office.

Unless otherwise noted, the electronic SAE application (eSAE) will be utilized for safety reporting to the IND Office and MDACC IRB.

Serious adverse events will be captured from the time of the first protocol-specific intervention, until 30 days after the last dose of drug, unless the participant withdraws consent. Serious adverse events must be followed until clinical recovery is complete and laboratory tests have returned to baseline, progression of the event has stabilized, or there has been acceptable resolution of the event.

Additionally, any serious adverse events that occur after the 30 day time period that are related to the study treatment must be reported to the IND Office. This may include the development of a secondary malignancy.

The following SAEs are not subject to expedited reporting, but would still be included in the annual report via the SAE log.

- a. Infection or cytopenias leading to hospitalization or prolongation of hospitalization
Disease progression leading to death, life-threatening AE, hospitalization or prolongation of hospitalization, or disability.

Reporting to FDA:

- Serious adverse events will be forwarded to FDA by the IND Sponsor (Safety Project Manager IND Office) according to 21 CFR 312.32
- **It is the responsibility of the PI and the research team to ensure serious adverse events are reported according to the Code of Federal Regulations, Good Clinical Practices, the protocol guidelines, the sponsor's guidelines, and Institutional Review Board policy.**

6.2.2.2. Procedure in Case of Pregnancy

If a female subject or partner of a male subject becomes pregnant during the study dosing period or within 3 months from the discontinuation of dosing, the investigator should report the information to the study supporter as if it is an SAE. The expected date of delivery or expected date of the end of the pregnancy, last menstruation, estimated fertility date, pregnancy result and neonatal data etc., should be included in this information. The investigator will follow the medical status of the mother, as well as the fetus, as if the pregnancy is an SAE.

When the outcome of the pregnancy falls under the criteria for SAEs [spontaneous abortion, induced abortion, stillbirth, death of newborn, congenital anomaly (including anomaly in a miscarried fetus)], the investigator should respond in accordance with the report procedure for SAEs. Additional information regarding the outcome of a pregnancy (which is categorized as an SAE) is mentioned below.

- "Spontaneous abortion" includes abortion and missed abortion.
- Death of an infant within 1 month after birth should be reported as an SAE regardless of its relationship with the study drug.
- If an infant dies more than 1 month after the birth, it should be reported if a relationship between the death and intrauterine exposure to the study drug is judged as "possible" by the investigator.
- In the case of a delivery of a living newborn, the "normality" of the infant is evaluated at the birth.
- "Normality" of the miscarried fetus is evaluated by visual examination unless test results which indicate a congenital anomaly are obtained prior to miscarriage.

6.2.2.3. SAE Reporting to Study Supporter (GSK/Novartis)

Any serious adverse events which occur during the clinical study or within 30 days of receiving the last dose of study medication, whether or not related to the study drug, must be reported by the investigator. In addition, any SAEs which occur as a result of protocol specific diagnostic procedures or interventions must also be reported.

All serious adverse events must be reported by facsimile within 24 hours to Novartis Oncology. MDC – Oncology [contact] (make sure you include the 1 prior to the 610 as this is a desktop fax)

The SAE report should comprise a full written summary, detailing relevant aspects of the adverse events in question. Where applicable, information from relevant hospital case records and autopsy reports should be included. Follow-up information should be forwarded to Novartis Oncology within 24 hours.

SAEs brought to the attention of the investigator at any time after cessation of eltromboapg and considered by the investigator to be related or possibly related to eltrombopag must be reported to Novartis Oncology if and when they occur. Additionally, in order to fulfill international reporting obligations, SAEs that are related to study participation (e.g., procedures, invasive tests, change from existing therapy) or

are related to a concurrent medication will be collected and recorded from the time the subject consents to participate in the study until he/she is discharged.

6.2.3. Secondary Efficacy Endpoints

The key secondary endpoints for this study are:

- The incidence of transformation to AML by FAB during treatment period and follow-up
- The incidence and severity of bone marrow fibrosis during treatment period and follow-up
- Proportion of patients achieving a platelet response during treatment; and proportion of patients achieving a durable platelet response.
 - o Platelet IWG-2006: A complete response is defined as a platelet count $> 100 \times 10^9/L$; and a major response defined as an increase of platelet count by higher than $30 \times 10^9/L$.
 - o Durable platelet count: in which a hematologic improvement in platelets (HI-P) defined as either an increase $\geq 30 \times 10^9/L$ from patients with a baseline platelet count $\geq 20 \times 10^9/L$, or an increase from $< 20 \times 10^9/L$ to $\geq 20 \times 10^9/L$ and by at least 100%, present for ≥ 8 weeks.

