1.2 Secondary

The secondary objectives of the study are:

- Incidence of transformation from MDS to AML during treatment period and follow-up
- Incidence and severity of bone marrow fibrosis during treatment period and follow-up
- Proportion of patients achieving a platelet response during treatment per IWG-2006 criteria
- Proportion of patients achieving a durable platelet response during treatment per IWG-2006 criteria

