3. STUDY ELIGIBILITY

3.1 Inclusion Criteria

1. Signed, informed consent must be obtained prior to any study specific procedures.
2. Subjects with a histologically confirmed diagnosis of MDS by FAB criteria, including both MDS and RAEB-T (AML with 20-30% blasts and multilineage dysplasia) by World Health Organization (WHO) classification are eligible.
3. Patients must have completed at least 4 cycles of hypomethylating agent therapy (e.g azacitidine or decitabine) with failure to achieve at least a partial response, or with the presence of ongoing cytopenias per IWG (platelet count $< 100 \times 10^9/L$, hemoglobin $< 11g/L$ or ANC $< 1 \times 10^9/L$). Patients with progressive disease on HMA-therapy prior to this time point are also eligible at the time of documented progression. Therapy with decitabine analogs (i.e. SGI-110) will be considered as decitabine for the purposes of this study.
4. Platelet count $< 100 \times 10^9/L$
5. Low, intermediate-1, intermediate-2 or High-risk category by IPSS
6. Eastern Cooperative Oncology Group (ECOG) performance status of 0 to 2
7. Adequate liver function, as evidenced by a serum bilirubin $\leq 2x$ the ULN (except for patients with a confirmed diagnosis of Gilbert's Disease) and an ALT or AST $\leq 3x$ the laboratory ULN.
8. Serum creatinine $\leq 2x$ upper limit of normal
9. Subjects must be ≥ 18 years of age at the time of informed consent, because no dosing or adverse event data are currently available on the use of eltrombopag in children.

10. Subject is practicing an acceptable method of contraception (documented in chart). Female subjects (or female partners of male subject) must either be of non-childbearing potential (hysterectomy, bilateral oophorectomy, bilateral tubal ligation or post-menopausal > 1 year), or of childbearing potential and use one of the following highly effective methods of contraception (i.e. Pearl index < 1.0%) from 2 weeks prior to administration of study medication, throughout the study, and 28 days after completion or premature discontinuation from the study:

- Complete abstinence from intercourse;
- Intrauterine device (IUD);
- Two forms of barrier contraception (diaphragm plus spermicide, and for males condom plus spermicide);
- Male partner is sterile prior to entry into the study and is the only partner of the female;
- Systemic contraceptives (combined or progesterone only).

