6.2. Study Endpoints

6.2.1. Primary Efficacy Endpoint: The overall response rate (CR + PR + HI) based on the IWG-2006 criteria. Responses must last at least 4 weeks.

Complete Remission:

- Bone marrow: $\leq 5\%$ myeloblasts with normal maturation of all cell lines
- Persistent dysplasia will be noted
- Peripheral blood
 - o Hemoglobin $\geq 11\text{g/dL}$
 - o Platelets $\geq 100 \times 10^9/\text{L}$
 - o Neutrophils $\geq 1.0 \times 10^9/\text{L}$
 - o Blasts 0%

Partial Remission:

- All CR criteria if abnormal before treatment except:
 - o Bone marrow blasts decreased by $\geq 50\%$ over pretreatment but still $> 5\%$

Stable Disease:

- Failure to achieve at least PR, but no evidence of progression for >8 weeks

Failure:

- Death during treatment or disease progression characterized by worsening of cytopenias or significant increase in percentage of bone marrow blasts

Hematologic Improvement (HI) Response Criteria*: responses must last at least 8 weeks

- **Erythroid response** (if pretreatment hemoglobin $< 11\text{g/dL}$)
 - o Hemoglobin increase by $\geq 1.5\text{g/dL}$
 - o Relevant reduction of units of RBC transfusions by an absolute number of at least 4 RBC transfusions/8 wk compared with the pretreatment transfusion number in the previous 8 wks. Only RBC transfusions given

for a Hgb of ≤ 9.0 g/dL pretreatment will count in the RBC transfusion response evaluation

- **Platelet response** (if pretreatment platelets $< 100 \times 10^9/L$)
 - o Absolute increase of $\geq 30 \times 10^9/L$ for patients starting with $> 20 \times 10^9/L$ platelets
 - o Increase from $< 20 \times 10^9/L$ to $> 20 \times 10^9/L$ and by at least 100%
- **Neutrophil response** (if pretreatment $< 1.0 \times 10^9/L$)
 - o At least 100% increase and an absolute increase of $> 0.5 \times 10^9/L$

*Pretreatment counts averages of at least 2 measurements (not influenced by transfusions) for at least one week

Progression or relapse after HI‡:

- At least 1 of the following:
 - o At least 50% decrement from maximum response levels in granulocytes or platelets
 - o Reduction in hemoglobin by ≥ 1.5 g/dL
 - o Transfusion dependence
- ‡In the absence of another explanation, such as acute infection, repeated courses of chemotherapy (modification), gastrointestinal bleeding, hemolysis, and so forth. It is recommended that the 2 kinds of erythroid and platelet responses be reported overall as well as by the individual response pattern.

Relapse after CR or PR:

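### Plain platelet response in section 6.2.3 can be met by one unconfirmed count, and its definition agrees neither with section 6.2.1 nor with the durable endpoint beside it

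*Combined protocol and SAP*

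**What the plan says.** Section 1.2 lists as a secondary objective "Proportion of patients achieving a platelet response during treatment per IWG-2006 criteria". Section 6.2.3 names the key secondary endpoint as "Proportion of patients achieving a platelet response during treatment; and proportion of patients achieving a durable platelet response" and gives two categories of platelet response. For the first: "A complete response is defined as a platelet count $> 100 \times 10^9/L". For the second: "a major response defined as an increase of platelet count by higher than $30 \times 10^9/L".

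The only duration in 6.2.3 closes the definition of the durable endpoint: "and by at least 100%, present for ≥ 8 weeks". Inclusion criterion 4 in section 3.1 admits patients at any count below 100 ×10⁹/L, with no margin.

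Section 6.2.1 has its own platelet response under hematologic improvement (HI): "Absolute increase of $\geq 30 \times 10^9/L$ for patients starting with $> 20 \times 10^9/L$ platelets", or, from below 20, a rise to above 20 with at least a doubling. There "responses must last at least 8 weeks", and baseline is an average of at least two counts not influenced by transfusion.

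Section 8.4.2 drops platelet counts taken within 3 days of a transfusion. It reports binary secondary endpoints as proportions with exact 95% intervals.

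**The concern.** A patient who enters at 96 and once reads 102 is a complete platelet responder on a rise of 6. A patient at 60 who once reads 91 is a major responder. In both cases the highest of many counts decides. Section 5.3 schedules counts weekly in cycle 1 and until stable, then at each cycle. Nothing in 6.2.3 separates a chance excursion from a response.

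The two definitions of platelet response also give different answers for the same patient, and section 1.2 does not say which one applies.

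Eltrombopag is a platelet agent, and section 2.2 gives that mechanism as a reason for restricting entry to counts below 100. The platelet response rate will therefore be read closely. It is reported per arm, without a control, in arms chosen by patient and physician (section 5.2).

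**Working it through.** The plan states no expected rate for this endpoint, so there is no figure to reproduce. All counts are in ×10⁹/L.

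**1. Which requirements apply to which definition**

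| | Minimum change | Duration or repeat |
|---|---|---|
| 6.2.3 complete | none; count >100 | none |
| 6.2.3 major | rise >30 | none |
| 6.2.3 durable | rise ≥30 if baseline ≥20; otherwise to ≥20 and at least doubled | ≥8 weeks |
| 6.2.1 HI platelets | rise ≥30 if baseline >20; otherwise to >20 and at least doubled | ≥8 weeks |

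Durable response is not a subset of response. For a patient going from 10 to 25 for 8 weeks, the count reaches 20, has more than doubled (25/10 = 2.5) and lasts 8 weeks, so the response is durable. But 25 is not above 100, and the rise of 15 is not above 30, so it is not a platelet response.

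**2. Where the missing minimum rise matters**

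The smallest rise that gives a complete response is just over 100 − baseline: 5 from 95, 10 from 90, 20 from 80. At a baseline of 70 or below, any count above 100 is already a rise above 30. The >100 rule therefore adds responders only for baselines above 70 and below 100.

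**3. Response rate with no drug effect**

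Assumptions, none of them in the documents:
- Lognormal noise around an unchanged true level, within-patient CV 15–20%.
- Two pretreatment counts, both below 100, averaged as baseline.
- 6–9 independent on-treatment counts.

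Section 2.1 offers a loose anchor for baselines: 67% of referred MDS patients were below 100, and over 10% of lower-risk patients were below 20. Treating these as 67% and 10% of one lognormal population gives log-SD = ln(100/20)/(0.440 + 1.282) = 0.935 and median = 100 × exp(−0.440 × 0.935) = 66 before the entry cut. A lower-count alternative has median 30 and log-SD 0.7. A uniform baseline over 10–110 is an upper case with no basis in the documents.

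| Baselines | Any count >100 | Either branch | Only through >100 |
|---|---|---|---|
| Lognormal, median 66 | 8–13% | 9–18% | 3–5% |
| Lognormal, median 30 | 2–4% | 3–7% | about 1% |
| Uniform 10–110 | 13–20% | 15–26% | 5–8% |

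The either-branch rate is thus about 3–18% with lognormal baselines. With 23 patients per arm, 23 × 0.03 = 0.7 and 23 × 0.18 = 4.1, or about one to four patients. A correlation of 0.5 between successive counts hardly changes this (9–17% in the first row).

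**4. What drives it**

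In the first row, deleting the >100 rule would remove only 3–5 percentage points. The unconfirmed rise above 30 accounts for the rest: just over half of responders at the low-variability end and about four-fifths at the high end.

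**5. Effect of the HI-P (platelet HI) change on two consecutive counts**

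| Baselines | Independent counts | Correlation 0.5 |
|---|---|---|
| Lognormal, median 66 | 0.5–2.5% | 1.3–5.4% |
| Lognormal, median 30 | 0.1–0.8% | 0.3–1.9% |
| Uniform 10–110 | 0.7–3.7% | 1.8–7.3% |

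**The case against.** The best defence is that the consequence is limited. The endpoint is secondary and descriptive, and no test or stopping rule uses it. Durable response, with a minimum change and 8 weeks, is reported beside it. Section 8.4.2 already removes counts near a transfusion. At 23 patients per arm, a few noise responders sit inside a wide interval: 3 of 23 has an exact 95% interval of about 3–34%. All of this stands, and it limits the severity. It does not repair the definition, because an interval allows for sampling error and not for a criterion that chance can meet.

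The size is also open to challenge. The section 2.1 figures come from two different populations, neither of them patients who have failed a hypomethylating agent, and section 2.1 says severe thrombocytopenia is common on those agents. With lower baselines the rate falls towards 3%. That stands too, and is why the result is given as a range.

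One could answer that the 6.2.1 rule was meant to govern 6.2.3. That is weak: with 8 weeks attached, plain and durable platelet response would be practically the same endpoint.

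A reader might go the other way and blame mainly the match between the entry cut-off and the >100 rule, since noise is severe near 100. At a true level of 90, CV 15% and eight independent counts, 86% would exceed 100 at least once. But patients with a baseline mean of 80 or more are only about 8–9% of entrants under the median-66 fit, and at a true level of 50 or below the effect is practically nil.

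**Conclusion.** The concern holds as a fault of definition in a key secondary endpoint. Plain platelet response needs one untransfused count in either branch, conflicts with the platelet response in 6.2.1, and can exclude a durable responder. These points follow from the text alone.

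The size is conditional: about 3–18% responders with no drug effect for lognormal baselines, and up to about 26% under the uniform baseline. The missing minimum rise contributes about 1–5 percentage points under lognormal baselines; the lack of confirmation is the larger part.

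A reader might infer that the trial's efficacy decision is compromised, particularly since sections 1.1, 4.1 and 8.1 count major hematologic improvement in the primary endpoint and 6.2.3 uses the word major. The documents do not support that. Section 6.2.1 spells out the platelet criterion for the primary endpoint with a minimum change and 8 weeks, and the Simon rules in 8.2.1 use the overall response rate only. What is at risk is an inflated descriptive proportion. The change should be made, but the design does not depend on it.

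**What to change.** In section 6.2.3:
- Define platelet response by the change already written for the durable endpoint: a rise of at least 30 ×10⁹/L if baseline is 20 or more, or a rise to at least 20 with at least a doubling if baseline is below 20.
- Measure it against the averaged pretreatment count described in 6.2.1.
- Require it on at least two consecutive counts at least 1 week apart, keeping the transfusion exclusion of 8.4.2. The one-week interval is a proposal; the documents' own durations are 4 and 8 weeks.
- Report a count above 100 only as a sub-category of these responders.

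Then reconcile sections 1.2, 6.2.1 and 6.2.3, so that the IWG-2006 label refers to one platelet change with stated durations and the boundary at exactly 20 is treated alike. Every durable responder will then also be a platelet responder, provided the counts are taken.

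The cost is a wording change using counts already scheduled. The reported rate will be somewhat lower. Confirmation reduces noise responders without eliminating them: with lognormal baselines and successive counts correlated at 0.5, from under 0.5% to about 5% remain.

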8.4.2. Analysis of Key Study Endpoints

The primary endpoint is overall response rate (ORR). The ORR in each arm will be evaluated along with the exact 95% confidence interval. Given the limited sample size, no formal comparison will be made between these two arms in terms of ORR.

Secondary endpoints include platelet response, durable platelet response, transformation to AML, incidence of bone marrow fibrosis, and time-to-event outcomes such as progression-free survival (PFS) and overall survival (OS). The probabilities of PFS and OS will be estimated using the method of Kaplan and Meier. The incidence rates of other binary secondary endpoints will be estimated, along with the exact 95% confidence intervals. Subjects that discontinue the study prior to having achieved a clinical response will be considered to have not had an event.

Patients receiving growth factors other than eltrombopag (erythropoietin, GM-CSF or G-CSF) will not be considered in the HI analysis for the time periods specified in Section 4.5.3 Supportive Care Guidelines. Hemoglobin levels and platelet counts collected from patients that have received a transfusion within the last 3 days will not be considered in the analysis.

Survival or times to failure and time to progression functions will be estimated using the Kaplan-Meier method. The two-sided log-rank test will be used to assess the differences of time to events between groups.

The total number of dose administrations, the average dose (mg), and the cumulative dose administered will be summarized by eltrombopag treatment group.

Blood chemistry and complete blood counts will be summarized by treatment group at each time point.

Additional exploratory analyses of the key study endpoints will be performed as deemed appropriate.

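### Section 6.2.3 defines platelet response with no branch for baselines below 20, so a durable platelet responder can be counted as a platelet non-responder

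*Combined protocol and SAP*

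**What the plan says.** All counts here and below are in units of 10^9/L.

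Section 6.2.3 of the combined protocol and SAP lists two platelet endpoints together: "Proportion of patients achieving a platelet response during treatment; and proportion of patients achieving a durable platelet response". It gives each its own rule.

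- **Platelet response.** A complete response is a count above 100, "and a major response defined as an increase of platelet count by higher than" 30. Neither category depends on baseline, and no duration is given.
- **Durable platelet response.** This is the state "in which a hematologic improvement in platelets (HI-P) defined as either an increase" of at least 30 from a baseline of at least 20, or a rise from below 20 to at least 20 that is also at least a doubling, present for 8 weeks or more.

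Section 1.2 names both endpoints by reference to IWG-2006 without thresholds, for example "Proportion of patients achieving a durable platelet response during treatment per IWG-2006 criteria". Section 6.2.1 has a separate platelet criterion within hematologic improvement (HI), which feeds the primary endpoint. That criterion does have a below-20 branch, but its cut-offs are above 20 and below 20, so a baseline of exactly 20 has no category. Section 6.2.3 does not refer to it.

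Section 8.4.2 redefines neither platelet endpoint and says: "The incidence rates of other binary secondary endpoints will be estimated, along with the exact 95% confidence intervals".

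**The concern.** A durable response is naturally read as a response that lasts, so durable responders should be contained in the responders. Under the two rules in 6.2.3 they are not. The response rule lacks the low-baseline branch, and it uses a strict inequality at 30 where the durable rule does not.

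Take a patient with baseline 10 whose count is held at 25 for 8 weeks. The HI criterion in 6.2.1 credits this patient towards ORR on platelet grounds, and the durable rule in 6.2.3 credits the patient too. The platelet-response rule does not: 25 is not above 100, and a rise of 15 is not above 30.

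The gap falls on the most thrombocytopenic patients. Section 3.1 admits any count below 100, and Section 2.1 reports counts below 20 at presentation in over 10% of patients even in lower-risk MDS (background, not a forecast for this trial). If the rules are programmed as written, the two reported proportions cannot be read as a set and its subset, and the response rate can miss patients whom the durable rate includes.

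**Working it through.** The plan states no power or error rate for these endpoints, so there is no figure to reproduce. The check compares the rules directly.

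**Rules.** Let b be the baseline and c an on-treatment count unaffected by transfusion.

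- Response (6.2.3): c > 100, or c − b > 30.
- HI-P count rule (6.2.3, durable if held for 8 weeks or more): b ≥ 20 and c − b ≥ 30; or b < 20, c ≥ 20 and c ≥ 2b.

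**Baselines below 20.** HI-P starts at c = max(20, 2b). Response starts at the first whole number above b + 30.

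| Baseline | Smallest count, HI-P | Smallest count, response | HI-P but not response |
|---|---|---|---|
| 5 | 20 | 36 | 20–35 |
| 8 | 20 | 39 | 20–38 |
| 10 | 20 | 41 | 20–40 |
| 15 | 30 | 46 | 30–45 |
| 19 | 38 | 50 | 38–49 |

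The width of the gap is (b + 30) − max(20, 2b) + 1. For b = 1 to 10 this is b + 11, which sums to 55 + 110 = 165. For b = 11 to 19 it is 31 − b, which sums to 279 − 135 = 144. The total is 309 whole-number baseline/count pairs. No pair at these baselines meets response without HI-P, so here the mismatch runs one way. A patient is durable-only if the HI-P criteria hold for 8 weeks and no evaluable count ever exceeds b + 30.

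**Baselines of 20 or more.** The only durable-only pairs are rises of exactly 30 (c = b + 30 ≤ 100), which gives 51 pairs at b = 20 to 70. Section 6.2.1 averages the baseline: "Pretreatment counts averages of at least 2 measurements (not influenced by transfusions) for at least one week". With half-unit baselines from 20.5 to 70.5 a whole-number count cannot give a rise of exactly 30, and the two rules agree at all 51 baselines. This edge is minor.

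**Opposite direction.** Response without HI-P occurs at b = 72 to 99, for c = 101 to b + 29. The number of pairs is the sum of (b − 71) = 1 + 2 + … + 28 = 406.

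**Durable-only pairs left after each change** (309 + 51 = 360 to begin with):

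- Change above 30 to at least 30, alone: 360 − 51 − 19 = 290.
- Add the below-20 branch, alone: 51.
- Both: 0.

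Pair counts show where the rules disagree. They are not patient frequencies.

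**Effect on the two rates.** With r responders, of whom t are not durable, and d durable-only patients among n:

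durable rate − response rate = (r − t + d)/n − r/n = (d − t)/n.

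The durable rate exceeds the response rate only if d > t, and t includes every response shorter than 8 weeks and every count above 100 without HI-P.

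Illustration with assumed numbers, n = 23, r = 4, t = 1, d = 2:

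- Response as written: 4/23 = 17.4% (exact 95% CI 5.0–38.8).
- Durable: 5/23 = 21.7% (7.5–43.7).
- Response after both changes: 6/23 = 26.1% (10.2–48.4), which contains the five durable responders.

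**6.2.1 against 6.2.3.** The two HI-P count rules differ only at a baseline of exactly 20 (for c ≥ 50) and at a count of exactly 20 from baselines of 1 to 10.

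**The case against.** The strongest reply is that the intended meaning can be recovered. Section 1.2 invokes IWG-2006, the 6.2.1 platelet criterion already has a below-20 branch, and 6.2.3 never says that its complete and major categories exhaust platelet response. This makes it likely that the branch was intended. It does not settle the matter: 6.2.3 prints its own thresholds under an IWG-2006 label, makes no reference to 6.2.1, and the 6.2.1 criterion carries an 8-week requirement that the 6.2.3 response rule lacks. A programmer following 6.2.3 would code the gap.

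It is also fair that no section says the durable group must be nested in the response group, that the durable-only band is fairly narrow, and that the illustration was chosen to show the reversal. For those reasons no probability is claimed.

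Two further points stand in part. The fix leaves all 406 response-without-HI-P pairs, such as a baseline of 95 reaching 101. They do not break the nesting, because they add to response and not to durable response. The fix also leaves platelet response without a stated minimum duration, so one untransfused count of 20 from a baseline of 10 would then qualify. That omission is already in the plan: today a single count more than 30 above baseline qualifies.

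**Conclusion.** The concern holds. As written, 6.2.3 can classify the same patient as a durable platelet responder and a platelet non-responder. The substantive gap is at baselines below 20; the exactly-30 and exactly-20 edges are minor.

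The rule comparison assumes only that counts are held long enough and are free of transfusion effect. The number of patients affected is unknown because the documents give no baseline platelet distribution for this trial. In an arm of 23, each such patient lowers the reported response rate by 1/23 = 4.3 percentage points.

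The consequence is limited to untested secondary proportions. The thresholds of 3 of 23 and 4 of 23 in Section 8.2.1 rest on ORR, which uses the 6.2.1 criterion and not the 6.2.3 response rule, so this gap does not affect them. The point should be corrected, but it does not threaten the primary analysis.

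**What to change.** In 6.2.3, make two changes to the platelet-response rule:

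1. Require a rise of at least 30 instead of more than 30.
2. Add the durable rule's low-baseline branch: from below 20 to at least 20, and at least doubled.

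Durable response is then the HI-P criteria held for 8 weeks or more, and is a subset of response by construction. The above-100 category can stay. Both changes are needed, since either one alone leaves durable-only cases.

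Separately, use the same cut-offs at 20 in 6.2.1 and 6.2.3, so that a baseline of exactly 20 has a platelet category in both. If 6.2.1 takes the 6.2.3 cut-offs, this amends a component of the primary endpoint and should be recorded as such. It changes HI-P there only for a baseline of exactly 20, or a count of exactly 20 from baselines up to 10, and in both cases it can only add responders.

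The cost is two wording changes and one alignment, with no new data or visits. The drawback is that the platelet-response rate can only stay the same or rise, so the change should be made and dated before the response data are analysed.
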